PROWL	Patient reported outcome in laser-assisted in situ keratomileusis
SE	Spherical equivalent
SW	Software
UCNVA	Uncorrected near visual acuity
UDVA	Uncorrected distance visual acuity
UADE	Unanticipated adverse device effect
Z80.11	ANSI Standard – Laser Systems for Corneal Reshaping

NOTE: The first occurrence of some abbreviations is not spelled out in the document (e.g., units of measure).

2. SYNOPSIS

Bausch + Lomb Study #884		
Title:	A Study to Investigate the Effectiveness of the TENEO 317 Model 2 (1.28 US) Excimer Laser for Laser In Situ Keratomileusis (LASIK) Surgery to Treat Myopia or Myopic Astigmatism	
Phase of study:	Pivotal IDE Study for Effectiveness	
Number of study centers and subjects:	Up to twelve (12) clinical centers in the United States. Approximately 334 subject eyes will be treated with a target of 300 operative (study) eyes completing the study.	
Objectives:	To evaluate the effectiveness of the TENEO 317 Model 2 (1.28 US) Excimer Laser in Laser In Situ Keratomileusis (LASIK) surgery for myopia or myopic astigmatism	
Indications for use:	Myopia: -1.00 to -10.00 D Astigmatism: 0.0 D to -3.0 D MRSE Treated: -1.0 D to -11.50 D	
Study design:	This will be a multicenter, prospective, open label, non-randomized, single arm study evaluating the safety and effectiveness of the Technolas TENEO 317 Model 2 (version 1.28 US software) Excimer Laser when used in LASIK surgery to treat myopia or myopic astigmatism. Both eyes of a subject may be enrolled so long as both eyes meet all inclusion/exclusion requirements.	
	The study purpose, procedures, and subject responsibilities will be explained to the potential participant. The subject's willingness and ability to meet the follow-up requirements will be determined. When it has been established that the subject appears to be eligible and willing to participate, written informed consent (which includes consent to have photo and video recordings of the eye surgery made) will be obtained. Written informed consent will be obtained from each study subject prior to performing any study specific procedures which include items which are NOT part of the Investigator's routine standard of care. In addition, written informed consent must be obtained prior to the day of surgery. A complete ophthalmic examination will be done at the Pre-Operative Visit scheduled within 60 days prior to surgery. All enrolled subject eyes that meet eligibility criteria will be seen according to the following schedule:	

Bausch + Lomb Study #884	
	 Visit 1: Pre-operative (1 to 60 days prior to treatment) Visit 2: Operative (Day 0) Visit 3: Initial Post-Op (Day 1) Visit 4: One Week (Day 5-9) Visit 5: One Month (3 to 5 weeks post-op) Visit 6: 3 Months (10 to 14 weeks post-op) Visit 7: 6 Months (21 to 26 weeks post-op) Visit 8: 9 Months (35 to 43 weeks post-op) A 180-Day premarket approval (PMA) supplement will be submitted to the US Food and Drug Administration (FDA) when all subjects have exited the study.
Number of Subject Eyes Planned	Sponsor intends to treat approximately 334 eyes, with anticipation to have 300 eyes after a 10% dropout rate evaluable for safety and effectiveness post-LASIK surgery at the time refractive stability is achieved ¹ . It is planned to have ≥ 20 subject eyes per dioptric bin (i.e., per column and row for presentation of preoperative refractive error by sphere and cylinder) over the spherical correction range to be studied and ≥ 30 subject eyes per dioptric bin over the cylinder correction range to be studied. Of the subjects in the -0.25 to -1.0 D astigmatism range, at least 30 eyes are planned in each of the -0.25 to -0.5 D and the -0.5 to -1.0 D astigmatism ranges. (See also Section 5.2)
Inclusion Criteria	 This study will include subjects who meet all of the following inclusion criteria: 1. Are 22 years of age or older. 2. Have read, understood, and signed an informed consent form (ICF). 3. Have demonstrated stable refraction (i.e., a change of ≤±0.5 D in sphere and cylinder) for a minimum of 12 months prior to surgery verified by consecutive refractions, medical records or prescription history.

¹⁴ Refractive stability for the study cohort is defined as a minimum of 95% of eyes that should have a change of ≤ 1.00 D of manifest refraction spherical equivalent between two refractions performed at least 3 months apart.

	Bausch + Lomb Study #884
	 Have myopic refractive error with or without astigmatism; sphere -1.0 D up to -10.00 D, cylinder between 0.0 D and -3.0 D; with a manifest refraction spherical equivalent (MRSE) between -1.0 D and -11.50 D. Have uncorrected distance visual acuity (UDVA) of 20/40 or worse Have manifest, distance best spectacle corrected visual acuity (BSCVA) of 20/25 (logMAR 0.1) or better in an operative eye. Have equal to or less than 0.50 D spherical equivalent (SE) difference between cycloplegic and manifest refractions at Visit 1 (Pre-operative). Have normal corneal topography as determined by the Investigator.
	9. Have discontinued use of contact lenses for at least 2 weeks (for hard or toric lenses) or 3 days (for soft contact lenses) prior to the pre-operative examination, and through the day of surgery.
	10. All contact lens wearers must demonstrate a stable refraction (within \pm 0.5 D), as determined by MRSE, on two consecutive examinations at least 1 week apart, in an eye to be treated and the axis of cylinder should not differ by more than 15 degrees from the baseline cycloplegic refraction.
	11. Have the ability to lie flat without difficulty.
	12. Are willing and able to comply with the schedule for all post-surgery follow-up visits.
Exclusion Criteria	This study will exclude subjects who meet any of the following exclusion criteria:
	 Subjects for whom the combination of their baseline corneal thickness and the planned operative parameters for the LASIK procedure would result in treatment depth less than 250 microns from corneal endothelium.
	 Eyes for which the baseline manifest subjective refraction exhibits a difference greater than 0.50 D in sphere power, or a difference greater than 0.50 D in cylinder power, or a difference in cylinder axis of more than 15 degrees compared to the baseline cycloplegic subjective

Bausch + Lomb Study #884		
	refraction. For manifest cylinder of less than 0.50 D, the difference in cylinder axis will not be taken into consideration.	
3.	Subjects for whom the pre-operative assessment of the cornea indicates that one or both eyes are not suitable candidates for treatment based upon the Investigator's medical judgment.	
4.	Have evidence of retinal vascular disease.	
5.	Have a history of or have active corneal disease or infection (e.g., recurrent corneal erosion syndrome, herpes simplex or herpes zoster keratitis, etc.) in either eye.	
6.	Have a known sensitivity to any study medication.	
7.	Have central corneal scars affecting visual acuity or unstable keratometry with irregular mires in an eye considered for eligibility.	
8.	Have keratoconus, subclinical or forme fruste keratoconus, corneal dystrophy or other corneal irregularity (e.g., irregular astigmatism).	
9.	Have visually significant or progressive cataract in an eye considered for eligibility.	
10.	Had previous intraocular or corneal surgery in an eye considered for eligibility that might confound the outcome of the study or increase the risk to the subject.	
11.	Use chronic medications by any administration route that may increase risk to the subject or may confound the outcome of the study, including those known to affect wound healing (e.g., corticosteroids, antimetabolites, etc.).	
12.	Are known to have acute or chronic disease or illness (e.g., dry eye, cataract, glaucoma, immuno-compromised, rheumatoid arthritis, clinically significant atopic disease, acne rosacea, etc.) that would increase operative risk or confound the results of the study.	
13.	Are taking medications contraindicated with LASIK such as isotretinoin (Accutane) or amiodarone hydrochloride (Cordarone).	
14.	Are known to be pregnant, lactating, or who plan to become pregnant during the course of the study.	

Bausch + Lomb Study #884	
	15. Have known sensitivity to medications used for standard LASIK.
	16. Have the presence of systemic disease likely to affect wound healing, e.g., autoimmune disease, systemic connective tissue disease, diabetes, or severe atopic disease.
	17. Are participating in any other ophthalmic clinical trial within30 days of screening or during this clinical trial.
	 Have an ocular muscle disorder including a strabismus or nystagmus, or other disorder affecting fixation.
	19. Have a history of or evidence of glaucoma or are a glaucoma suspect.
	20. Eyes with mesopic pupil size > 7.0 mm.
	21. Have a Schirmer's pre-operative test without anesthesia < 4 mm/5 minutes
Planned Study Period and Duration of Treatment	Enrolled subject eyes will undergo LASIK surgery and will be followed for approximately nine months after surgery.
Test Medical Device	Technolas TENEO 317 Model 2 excimer laser is a scanning excimer laser that operates at 193 nm ultraviolet wavelength to photoablate corneal tissue in order to achieve a refractive change.
Study Effectiveness Endpoints	 The percentage of eyes that achieve predictability (attempted versus achieved) of MRSE within ± 0.50 D The percentage of eyes that achieve predictability (attempted versus achieved) of MRSE within ± 1.00 D The percentage of eyes targeted for emmetropia that achieve a UDVA of 20/40 or better
Statistical Methods	Continuous measures will be summarized by the mean, standard deviation, median, minimum, and maximum. Categorical and incidence measures will be summarized by both count and percentage.
	Following multiple imputations of missing data, each primary endpoint will be compared to a corresponding null proportion using a binomial test.
Sample Size Calculation	The study will involve an evaluation of approximately 334 treated eyes at up to 12 investigational sites. A final sample size of at least 300 evaluable study eyes at the final visit (Visit 8, Month 9) will be analyzed. ANSI Z80.11-2012 (R2017) recommends a sample size of

TENEO 317 1.28 US

Bausch + Lomb Study #884				
	300 treated eyes when there is a change to the indication (treatment range); the additional 34 study eyes will allow for losses up to 10% due to early subject discontinuation.			

This study will be performed in compliance with ISO 14155, including the archiving of essential study documents. This investigational plan follows guidelines outlined in the U.S. Food and Drug Administration (FDA) guidance entitled *Checklist of Information Usually Submitted in an Investigational Device Exemptions (IDE) Application for Refractive Surgery Lasers dated October 1996*, and elements of the international ANSI standard Z80.11-2012 (R2017) entitled *Laser Systems for Corneal Reshaping* and the ANSI, IEC, and ISO standards referenced therein. All data furnished to the investigator and his/her staff, and all data obtained through this study, will be regarded as confidential and proprietary in nature and will not be disclosed to any third party, except for the FDA or other regulatory body, without written consent from the Sponsor.

3. INTRODUCTION

The Technolas Teneo 317 Model 2 (ver. 1.28 US software [SW]) excimer laser is a scanning excimer laser that operates at the 193 nm ultraviolet wavelength to photoablate corneal tissue and employs a proprietary aspheric ablation profile rather than a conventional "Munnerlyn" ablation profile. By scanning a small diameter beam (1 mm in diameter), the Teneo 317 Model 2 (ver. 1.28 US SW) excimer laser offers the following advantageous features:

- Flexible treatment patterns for the treatment of myopia
- Wide ablation zones (up to 7 mm), and
- A smooth ablation surface

3.1 Epidemiology of Myopia and Myopic Astigmatism and Treatment

Myopia and myopic astigmatism are recognized as serious public health problems, with approximately 2.5 billion people expected to be myopic by the year 2020. ¹ There are a number of treatments available for treating myopia and myopic astigmatism, including eyeglasses, contact lenses, surgery, pharmaceutical treatments, and, within the past 25 years in the United States, wide use of refractive surgery (notable, laser in situ keratomileusis [LASIK] surgery). Although anisometropia, predominantly myopia, may occur in young children as early as age 6, refractive surgery in the pediatric population is generally discouraged and LASIK surgery in the United States (US) is not approved by the US Food and Drug Administration for people 18 years of age or younger. The FDA also warns that LASIK surgery may not be appropriate for people in their 20s and younger.²

A number of epidemiological studies and clinical studies have reported the demographics of myopia patients. It is recognized that comparisons of data for myopia patients globally is influenced by a number of factors including age, country, sex, race, ethnicity, occupation, environment, life style, and complex genetic factors. ³ The statements in this section are consequently not comprehensive and only intended to indicate general trends that have been seen in selected papers and reviews.

Global studies of myopia patients show some similarities in various regions. In the US, Western Europe, and Australia, the prevalence of myopia of at least -1.0 D in a survey of 29,281 persons 40 years of age and older was estimated as 25.4%, 26.0%, and 16.4% in 2000. ¹ In the same survey, patients with at least -5.0 D of myopia (higher myopes) represented 4.5%, 4.6%, and 2.8% of patients. ¹ A survey of the prevalence of refractive errors in occupants of Singapore in the Singapore Epidemiology of Eye Disease (SEED) Study, a multiethnic Asian population, gave rates among adults 40 years of age and older similar to that seen for the US, Western Europe, and Australia: 38.9% for myopia, 8.4% for high myopia, and 58.8% for astigmatism. ⁴

The gender distribution of myopia patients or myopia patients undergoing LASIK surgery generally favors a similar number of women and men, $^{4-6}$ with some reviews contrarily suggesting a preponderance of women over men by prevalence or by patients undergoing LASIK surgery. 1,7 With regards to ethnicity, a 2009 review of Americans between the ages of 12 and 54 years undergoing revealed Asians had the highest prevalence of myopia (18.5%), followed by Hispanics (13.2%), African-Americans (6.6%) and Caucasians (4.4%). ⁸

Refractive LASIK surgery patients in large retrospective clinical trials were relatively young in studies done in the UK (mean age 35.6 years), ⁵ Israel (mean age 29.9 years), ⁶ and Iran (mean age 29.4 years). ⁷ There also is a trend for younger myopia patients in the US and Singapore, with myopia rates dropping by decade for both men and women in multiple ethnic groups analyzed. ^{1,4} However, a necessary condition for refractive surgery is stable refraction, which typically does not occur until 18-22 years of age,⁹ which suggests a lower age limit for LASIK patients to be the onset of adulthood.

Most myopia patients undergoing LASIK surgery will likely have some degree of astigmatism ≥ -0.25 cylinder error). In a retrospective study in Iran, 11550 cases of compound myopic astigmatism (≥ -0.25 sphere, ≥ -0.25 cylinder error) were noted, while there were only 827 cases of simple myopia (≥ -0.25 sphere, no cylinder error).⁷ In other data on myopic astigmatism, there were increases over time in rates of myopia and astigmatism in the SEED study, ⁴ with 72% of the increase in the rate of astigmatism due to myopic astigmatism.

In summary, the epidemiology and demographics from large retrospective studies of myopia and myopic astigmatism indicate that LASIK patients in the US are equally likely to be men or women, include adult age groups, and are likely to have both sphere and cylinder refractive error. Although minority populations have a higher rate of myopia in the US, their possible under-representation or even over-representation in this study cannot be predicted without a proper understanding of the demographics of patients serviced by the clinical sites and recruited as subjects for this study. Nevertheless, the present study does not have an adequate sample size to power analyses at this level of demographic stratification.

3.2 History of LASIK:

The first approach to myopic keratomileusis was developed by Barraquer in the 1960s.^{10,11} A corneal lenticule was harvested with a microkeratome and then frozen. The frozen lenticule was then reshaped into the desired refractive lenticule with a cryolathe, thawed and sutured in place with an eight-bite anti-torque suture.^{11,12} This microkeratome required a great deal of experience to get reproducible results and freezing the lenticule caused death of the keratocytes and in some cases haze in the tissue. Irregular astigmatism and the

TENEO 317 1.28 US

B+L Study # 884 Protocol Ver 8.0

potential for a lost lenticule were also problems with the technique.^{12,13} Krumeich later attempted a non-freeze keratomileusis but this technique also had variable results and poor predictability.

The development of the automated microkeratome by Luis Ruiz using a non-freeze technique brought reproducibility to the procedure. The technique involved creating two keratectomies. The first keratectomy created a planar cap, which was initially excised from the cornea but later was left hinged to prevent inadvertent loss of the cap. The second keratectomy was also planar and was performed with the same microkeratome by changing the interchangeable plates and adjusting the diameter of the second cut. When the cap was put back in place, it essentially sank into the depression created by the second keratectomy, creating a flatter corneal curvature. This technique is referred to as Automated Lamellar Keratomileusis or ALK.^{11,14} The cornea remained clear but there were technical difficulties with the refractive cut. Variability in the refractive keratectomy (second cut) thickness, diameter and centration led to overcorrection, undercorrection, or irregular astigmatism. To achieve the proper refractive keratectomy was achieved. Other variables included microkeratome blade quality, sharpness and width that also affected the predictability of the result.

In 1983, Photorefractive Keratectomy (PRK) using an Argon Fluoride (ArF) Excimer Laser was first suggested by Trokel and Srinivasan.¹⁵⁻¹⁸ In 1992, Burrato used an Excimer Laser in conjunction with ALK by harvesting a cap with the automated microkeratome and treating the stromal surface of the cap with an Excimer Laser and replacing it without the use of sutures.^{19,20} In 1994, Brint used Burrato's technique, treating the cap with an Excimer Laser, and in four eyes the ablation was performed in situ.²¹ They reported minimal corneal haze, good visual acuity and more predictable results than with a mechanical refractive cut.

In 1991, Pallikaris coined the term LASIK, an acronym which stands for 'Laser In-Situ Keratomileusis', and reported using an excimer laser for LASIK of high myopes.²² In 1994, he compared the LASIK technique with surface photorefractive keratectomy (PRK) and found in a small series that LASIK created less corneal haze, was more stable and had greater predictability than PRK.²³ Irregular astigmatism was noted in most of the LASIK eyes in the first two weeks but subsided by one month. LASIK also appeared to have the advantage over PRK with visual stabilization occurring earlier, with lesser tendency for regression. The PRK subjects required topical steroids for three months while the LASIK group required them for one month.

In 1992, the scanning spot excimer laser technique for the delivery of laser radiation for photoablation of corneal tissue began to appear in the literature.²⁴ Results from preclinical tissue studies demonstrated that optical scanning delivery of excimer laser energy produces

smooth and gradual ablations without step-like transition zones, and without thermal damage.²⁵⁻²⁸ The FDA approved the first broad-beam excimer laser system for laser assisted in-situ keratomileusis (LASIK) treatment of myopia/myopic astigmatism in 1998,²⁹ followed by the first scanning spot laser for PRK in 1999 ³⁰ and the first scanning spot laser for LASIK in 2000.³¹ Today, virtually all excimer lasers systems used to perform LASIK surgery rely on computer-controlled scanning spot technology.

3.3 Risk/Benefit Analysis of LASIK

The risks of performing LASIK on sighted eyes include improper correction, decrease in BSCVA, glare, halo, foreign body sensations, corneal scarring, corneal ulceration or perforation, intraocular infection, corneal decompensation, persistent corneal edema, hyphema, hypopyon, endophthalmitis, microbial keratitis,³² cataract, epithelium in the interface, lost / misplaced / misaligned flap, dry eye, or melting of the flap.

Steps taken to mitigate the risks associated with this protocol include

- enlisting only Investigators with prior training and experience in corneal refractive surgery, including experience with: (a) the use of femtosecond laser "flap makers" and (b) laser-assisted in situ keratomileusis (LASIK) ensuring that Investigators review and understand this investigational protocol; and
- monitoring the study for adherence to the protocol and verifying all incidences of adverse effects are reported. During the period when study procedures and/or study sites are interrupted by the COVID-19 pandemic (see Section 7.4.1.1), monitoring may occur remotely.

The principle benefit of an aspheric LASIK procedure is the potential freedom from or reduced dependence on spectacles (glasses) and/or contact lenses for the correction of refractive error. LASIK may be safer than contact lens wear in the long term.²³ Additional potential benefits include rapid visual recovery and stabilization of refraction, and reduced risk of iatrogenic corneal stromal irregularity due to scanning of small overlapping beam.

4. OBJECTIVE

The primary objective of this clinical investigation is to collect safety and effectiveness data for the Technolas Teneo 317 Model 2 excimer laser for Laser Assisted In-Situ Keratomileusis (LASIK) correction of myopia and myopic astigmatism. It is intended that the results of the study will be submitted to the U.S. Food and Drug Administration (FDA) in a 180-Day premarket approval application (PMA) supplement.

5. STUDY DESIGN

5.1 Justification of Study Design

The TENEO 317 Model 2 excimer laser workstation received CE Mark status in Europe in 2017 and is currently running version 1.28 software (SW). The difference between the EU version 1.28 and the version 1.28 US SW is that the version 1.28 US SW will have software treatment capabilities other than myopic LASIK with or without astigmatism that will be disabled on all Technolas TENEO 317 Model 2 systems to be used in this myopia/myopic astigmatism study.

A retrospective post-CE Mark chart review provides evidence of the safety and effective performance of the TENEO 317 Model 2 excimer laser running PROSCAN ver. 1.27.2 SW for completing LASIK surgeries on myopic eyes with or without astigmatism through 1 month of follow-up with 518 eyes treated at 10 sites in Europe, Middle East and Africa.³³ Of the 518 eyes enrolled in the chart review, 72 eyes had spherical myopia and 446 eyes had myopic astigmatism.

In the chart review report, 93% of subject eyes were 20/20 or better at ≥ 1 mo, and 99% were 20/32 or better at ≥ 1 mo. Further, 100% of subject eyes had uncorrected distance visual acuity of 20/40 or better post-surgery.

The Technolas TENEO 317 Model 2 aspheric ablation PROSCAN version 1.27.2 software was the subject of a post-market study that demonstrated excellent results for spherical correction and showed a slight under-correction for cylinder. As a result, the laser's internal cylinder conversion factor for the PROSCAN version 1.27.2 software was increased to compensate for cylindrical under-correction, while the spherical correction component remained unchanged. The resulting revised aspheric ablation PROSCAN version 1.28 US software is the subject of this study.

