6.5.6.3.1 Predictability and Refractive Stability Analyses

The following predictability and refractive stability descriptive summaries will be provided for each visit interval starting with the 1- to 3-month interval and continuing to the 6- to 9month interval for all treated eyes, eyes treated for spherical myopia, and eyes treated for astigmatic myopia unless otherwise specified. Stability analysis will be repeated for Consistent Cohort.

- Eyes that exhibit an absolute change of less than or equal to 0.50 D, 1.00 D, and 2.00 D of MRSE between two refractions performed at 1 month and 3 months, and between subsequent refractions performed at least 3 months apart.
- Mean overall change and change per month (calculated as, Difference in MRSE/ Duration in Months, where month = 30 days) in MRSE between consecutive scheduled visits as determined by a paired analysis, with 95% CIs around the mean rate of change based on t-distribution.
 - The mean rate of change in MRSE is expected to decrease monotonically over time, with a projected asymptote of zero or a rate of change attributable to normal aging.
 - The 95% CI for the mean rate of change in MRSE is expected to include zero or a rate of change attributable to normal aging.
- Mean (\pm SD) MRSE for the preoperative and each postoperative visit
- Proportion of eyes with residual astigmatic error (absolute shift from Preoperative Visit to each postoperative visit in manifest axis versus residual manifest cylinder magnitude calculated as postoperative cylinder value minus targeted cylinder value in categories of ± 0.5 D, ± 1.0 D, ± >1.0 D) will be presented in a table and also stratified by preoperative diopter of cylinder as specified in Table 1 at Month 1, Month 3, Month 6, and Month 9 for eyes treated for astigmatic myopia.
- Assessment of cylinder stability between two refractions performed at 1 month and 3 months, and between subsequent refractions performed at least 3 months apart for correction of spherocylindrical refractive errors, expressed as the proportion of eyes

with an absolute change in cylinder magnitude of 0.00 D, 0.01 D to 0.50 D, 0.51 D to 1.00 D, 1.01 D to 1.50 D, and >1.51 D.

- Vector magnitude correction analysis will be summarized including intended refractive correction (IRC), surgically induced refractive correction (SIRC) and correction ratio (CR) calculated as SIRC/IRC, as defined in the Eydelman M paper

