 [2] and also provided in the appendix. These data by study visit will be presented as continuous summary for all eyes treated for astigmatic myopia.
- Cylinder correction (non-vectorial) stratified by preoperative cylinder as specified in Table 1 for all eyes treated for astigmatic myopia will be summarized on a continuous scale in a table by study visit beginning at Month 1 for percent reduction of absolute IRC.

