6.5.6.5.1 Additional Effectiveness Analyses

The following effectiveness descriptive summaries will be provided at Month 1, Month 3, Month 6, and Month 9. Primary effectiveness endpoint data will be presented using 1.00 D ranges from -1.00 D to -12.00 D (based on Table 1, the maximum MRSE value that is allowed in the study is -11.5 D) and for preoperative MRSE > -7.0 D versus MRSE \leq -7.0 D).

- Percentage of eyes that achieve predictability of MRSE within ± 0.50 D
- Percentage of eyes that achieve predictability of MRSE within \pm 1.00 D

- Percentage of eyes that achieve UCDVA of 20/40 or better
- Percentage of all eyes that achieve predictability (targeted versus achieved) of MRSE within ± 2.00 D
- Percentage of all eyes targeted for emmetropia that achieve UCDVA of 20/12.5 or better, 20/16 or better, 20/20 or better, 20/40 or better
- Percentage of eyes not targeted for emmetropia that achieve UCDVA of 20/20 or better and of 20/40 or better.
- Percentage of eyes that achieve predictability of manifest spherical refraction within $\pm 0.50 \text{ D}, \pm 1.00 \text{ D}$, and $\pm 2.00 \text{ D}$ of intended manifest spherical refraction
- Percentage of eyes with predictability of manifest refraction astigmatism within \pm 0.50 D, \pm 1.00 D, and \pm 2.00 D of intended manifest cylindrical refraction
- Percentage of eyes that achieve an UCDVA equal to or better than preoperative BSCVA, including eyes that achieve an UCDVA equal to or better than 20/40 if the preoperative BSCVA was 20/20 or better
- Change from baseline in BSCVA by study visit
- Change from baseline in UCNVA and UCDVA
- Percentage of eyes that are overcorrected or under corrected by > 1.00 D or > 2.00 D MRSE
- Percentage of eyes that achieve a difference between postoperative and preoperative BSCVA of < -2 lines, -2 lines, -1 line, 0 lines, +1 line, +2 lines, and > +2 lines (line changes will be calculated as integer portion of change from baseline values of Early Treatment Diabetic Retinopathy Study [ETDRS letter] score collected on the CRF divided by 5)
- Percentage of eyes with CR of ≤ 0.5 D and ≤ 1.0 D
- Absolute shift in cylindrical axis from preoperative to postoperative visits of 0, <= 5, 5.1 to 10, 10.1 to 15, 15.1 to 30, and >30 deg.
- Eyes as a function of angle of cylindrical error (based on vector analysis. Refer to Appendix 1 for derivation):
 - Eyes with error of angle \ge -15° and \le +15°
 - Eyes with error of angle greater than $+15^{\circ}$

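### The tested software raised the cylinder factor, but the SAP reports no signed cylinder correction by preoperative cylinder bin

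*Protocol*

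**What the plan says.** Protocol 5.1 reports slight cylinder under-correction with software 1.27.2. In response, the "internal cylinder conversion factor for the PROSCAN version 1.27.2 software was increased to compensate for cylindrical under-correction"; sphere was not changed. The result, version 1.28 US, is the software under test. Table 1 in both documents plans at least 30 eyes in each cylinder bin, so results by amount of cylinder are a design aim.

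SAP 6.5.6.3.1 plans two summaries for astigmatic eyes by preoperative cylinder:

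- **Percent reduction.** "Cylinder correction (non-vectorial) stratified by preoperative cylinder as specified in Table 1", to be "summarized on a continuous scale in a table by study visit beginning at Month 1 for percent reduction of absolute IRC". No formula is given.
- **Residual astigmatic error.** A cross-classification of "absolute shift from Preoperative Visit to each postoperative visit in manifest axis versus residual manifest cylinder magnitude", the latter "calculated as postoperative cylinder value minus targeted cylinder value", in categories that pool the two signs.

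The same section plans a continuous summary of IRC, SIRC and CR (SIRC divided by IRC) by visit, for astigmatic eyes as one group. SAP 6.5.6.5.1 adds the percentage of eyes with CR at or below 0.5 and 1.0, printed with a dioptre unit, and "Percentage of eyes that are overcorrected or under corrected by > 1.00 D or > 2.00 D MRSE". Neither is by cylinder bin.

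Protocol 9.6.3.1 includes CR in a list of variables to be stratified by preoperative MRSE and by preoperative manifest cylinder power. SAP 6.6 states that the cylinder stratification of these variables will not be summarized and gives no reason.

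**The concern.** A single multiplier on cylinder was increased, so over-correction became possible where under-correction had been seen. The useful report is correction by cylinder amount with its direction. The SAP dropped the protocol's cylinder stratification of the direction-bearing ratio, while its own stratified correction row is direction-blind.

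The sign of the residual does not help. SAP 6.5.4.2 puts all cylinders in minus notation and states an emmetropic target for every eye. The residual is then zero or negative whichever way the correction missed.

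At stake is the clarity of the descriptive evidence on the software change, by bin. No hypothesis test depends on it.

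**Working it through.** **The plan's own figures.** The documents give no figure for cylinder over- or under-correction, so there is none to reproduce. The sample-size figures do reproduce (300/0.9 = 333.3, hence 334 eyes; power above 99.99% for each endpoint) and are not in dispute.

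**Formulas.** From SAP Appendix 1, with double-angle components and a zero target, IRC is the preoperative vector and SIRC = pre − post. Vertex adjustment is ignored here.

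- Percent reduction = 100 × (1 − |post|/|pre|). This is the standard magnitude form and is assumed.
- CR = |SIRC|/|IRC|.
- Along-axis error = (X_SIRC·X_IRC + Y_SIRC·Y_IRC)/|IRC| − |IRC|. Positive means over-corrected.

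**Two eyes by hand.** Both start at 2.00 D and end with 0.50 D. One keeps the original axis and the other ends 90° away.

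| | Same axis | 90° away |
|---|---|---|
| Percent reduction | 100(1 − 0.50/2.00) = 75% | 75% |
| SIRC along the intended axis | 2.00 − 0.50 = 1.50 D | 2.00 + 0.50 = 2.50 D |
| CR | 0.75 | 1.25 |
| Along-axis error | −0.50 D | +0.50 D |
| Axis shift | 0° | 90° |

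Percent reduction cannot separate the two eyes. CR, signed error and axis shift can.

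**Simulation with measurement noise.** 400,000 eyes per setting. Residual vector = C(1 − g) plus noise on two components, magnitude rounded to 0.25 D, where g is the true fraction corrected. Noise SD of 0.15 to 0.25 D per component is assumed, and ranges below span it. Axis shift is taken as 0–90°, among eyes with a non-zero residual. The 30° cut comes from the axis categories in SAP 6.5.6.5.1, because the cross-classified table states none.

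| Cylinder C | g | Mean % reduction | Shift > 30° | Along-axis error C(g − 1) |
|---|---|---|---|---|
| 3.00 D | 0.85 | 82–84 | 1–9% | −0.45 D |
| 3.00 D | 1.00 | 90–94 | 67% | 0 |
| 3.00 D | 1.15 | 82–84 | 99–100% | +0.45 D |
| 2.00 D | 0.85 | 79–83 | 6–22% | −0.30 D |
| 2.00 D | 1.00 | 84–91 | 67% | 0 |
| 2.00 D | 1.15 | 79–83 | 95–100% | +0.30 D |
| 0.50 D | 0.85 | 36–60 | 44–55% | −0.075 D |
| 0.50 D | 1.00 | 37–63 | 67% | 0 |
| 0.50 D | 1.15 | 36–60 | 77–85% | +0.075 D |

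Percent reduction is symmetric about exact correction. Axis shift separates the directions well at 2.00 and 3.00 D and weakly at 0.50 D. Exact correction itself puts about two thirds of non-zero residuals above 30°, because a small residual has an essentially random axis.

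**A second noise model.** With CR SD 0.15, angle-error SD 5° and no rounding (all assumed), mean CR of 0.80 and 1.20 give mean reductions of 73.2% and 71.6%. With no angle error both give 78.7%. The share of eyes with CR above 1 is 9% against 91%.

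**Pooling.** Four equal-sized bins with CR 1.2, 1.1, 0.9 and 0.8 average (1.2 + 1.1 + 0.9 + 0.8)/4 = 1.0. CR is also biased upward by noise at low cylinder: at 0.50 D, exact correction reads 1.05–1.14 under the simulation above. This is a reason to report the signed error beside it.

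**MRSE.** A cylinder error of e shifts MRSE by e/2 when the power error lies only in the treated meridian. A 20% over-correction of 3.00 D is 0.60 D of cylinder and 0.30 D of MRSE, well inside the 1.00 D threshold of the over-/under-correction row.

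**The case against.** The strongest reply is that the SAP is not blind to direction.

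- The residual-error table is by preoperative cylinder and crosses the residual with axis shift. The two hand-worked eyes fall at 0° and 90°, so that table can tell them apart.
- CR is reported for all astigmatic eyes. The complement of the share at or below 1.0 is the share over-corrected in magnitude.
- Protocol 5.1 describes one conversion factor. A uniform overshoot from it would show in pooled CR. Cancellation needs opposite errors in different bins, which the documents do not suggest.
- In minus notation an over-corrected eye also shows positive sphere, and sphere predictability is tabulated.
- These are descriptive tables, and eye-level listings and datasets allow any signed analysis later.

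Most of this stands. A reader might infer that over-correction cannot be told from under-correction anywhere in the planned output, or that the report would invite a further increase of the factor. The documents support neither, because axis shift and pooled CR would both reveal a uniform overshoot.

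What the reply does not supply is a signed measure by bin. Axis shift is imprecise where cylinder is low or correction is near exact, and it gives no amount in dioptres. The sphere and CR rows lost their cylinder stratification in SAP 6.6.

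**Conclusion.** The point holds in a limited form. The SAP plans no signed cylinder correction by preoperative cylinder bin, although the change in the tested software concerns cylinder correction. The stratified percent-reduction row reads the same for equal over- and under-correction (82–84% for 15% either way at 3.00 D). Direction by bin must be inferred from axis shift, which is good at 2.00–3.00 D and weak at 0.50 D (44–55% against 77–85%, with about 67% at exact correction). Pooled CR would show a uniform error but could hide opposite errors across bins.

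This rests on the standard formula for percent reduction, a zero cylinder target as SAP 6.5.4.2 states (Protocol 7.1.2.2 only strongly recommends emmetropia), the borrowed axis cut, and the assumed noise. The symmetry of percent reduction without axis error does not depend on the noise.

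Primary endpoints, sample size and success criteria are unaffected. This is a cheap improvement to descriptive reporting, not a flaw in the trial's main inference.

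**What to change.** - **SAP 6.5.6.3.1:** keep the percent-reduction row and state its formula. Add, by Table 1 cylinder bin and visit for astigmatic eyes, CR (mean, SD, percentage above 1) and the signed along-axis error, (X_SIRC·X_IRC + Y_SIRC·Y_IRC)/|IRC| − |IRC|, in dioptres.
- **SAP 6.6:** restore the cylinder stratification of CR from Protocol 9.6.3.1.
- **SAP 6.5.6.5.1:** remove the dioptre unit from the CR cut-offs, since CR is a ratio.

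Appendix 1 already defines the vectors needed; the IRC components are preoperative minus target and equal the preoperative components when the target is emmetropia. The cost is SAP wording and one more descriptive table. No new data are needed.
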